Title:	Calibration Study of a Wearable Noninvasive Blood Alcohol Monitor
Population:	The present study will involve 12 men and women aged 21 to 55 who drink regularly and occasionally binge-drink. Women and minorities who meet the study criteria will be eligible to participate. No vulnerable populations are being targeted for inclusion in this study
Intervention:	Eligible subjects will receive alcohol in the laboratory setting. Subjects will complete a drinking session designed to raise BAL to 0.05 g/dL. Data from this drinking session will be used to calibrate wristwatch sensors with BAL measured by a breathalyzer. Subjects will return for a second drinking session following completion of the calibration trial. Data from this second trial will be used to validate the calibration model. During both drinking sessions subjects will have access to streaming entertainment. BAL will be measured continuously with wristwatch sensors, and every 15 minutes with a breathalyzer.
Objectives:	This NIH SBIR Phase II study addresses development of a new, noninvasive wrist-mounted device for measuring blood alcohol. This wristwatch platform with modern smartwatch capabilities will move the state of innovation forward in the noninvasive alcohol monitoring field and will contribute societal benefits in the form of facilitating alcohol research and treatment. Additional benefits include providing blood alcohol monitoring to consumers interested in health and fitness, employer wellness programs and other medical and judicial system uses. If successful, the transdermal alcohol sensor could be used in clinical research as an objective measure of drinking outcomes.
Design/Methodology:	This trial is designed to generate data that will be used to build a model that will transform transdermal alcohol readings into an approximate measure of breath alcohol level. The ultimate goal is to test the accuracy of a wristwatch BAL monitor relative to alcohol breath testing once this model has been completed. An established human laboratory self-administration procedure will be followed. Each subject will complete 4 clinic visits over a period of up to 9 months of participation. Study participation is comprised of 1) a baseline assessment to determine eligibility 2) an alcohol self-administration trial to develop a model for correlating transdermal alcohol with breath alcohol readings, 3) a follow-up assessment to confirm eligibility to continue, and 4) an

Calibration Study of a Wearable Noninvasive Blood Alcohol Monitor

Final V1.8 4.24.19

	alcohol self-administration trial to test the accuracy of the wristwatch BAL monitor .
Total Study Duration:	The entire study will take 12 months to complete.
Subject Participation Duration:	Each subject's length of participation will be up to 9 months.

3 Background/Rationale & Purpose

3.1 Background Information

The goal of this study will be to continue development and commercialization of a new noninvasive transdermal alcohol monitor developed by KWJ Engineering, Inc. The wrist-mounted transdermal ethanol measurement system being studied in this proposal is part of the modern trend toward wearable and noninvasive measurements. In recent years there has been a growing trend in science and technology toward developing noninvasive on-body, continuous measurements in the management of chronic disease, monitoring the elderly, diagnostic sensing and other biomedical applications [1-7]. Stretchable and flexible materials for dermal sensors are emerging, as are new approaches to making physical and chemical measurements noninvasively on the skin [8-11]. KWJ engineering is an industry-leading manufacturer of monitoring sensors, instruments, and gas sensors designed to reduce risks to health, safety, and security in commercial and consumer environments. KWJ has recently received an SBIR phase II award from NIAAA to continue efforts to develop a wearable transdermal sensor that monitors Blood Alcohol Level (BAL) in real-time. The monitor is based on the KWJ Engineering's printed electrochemical gas sensor that is able to detect ethanol concentrations in the skin. This ethanol sensor is a very small, ultralow power, and highly sensitive device with very low interferences. In previous studies leading up to the SBIR award, KWJ Engineering has demonstrated stable and sensitive measurement of ethanol across human skin surrogate membranes. This was accomplished with an initial prototype wristwatch device that included the ethanol sensor and circuitry for performing the measurement and converting data for wireless communication to a computer. Raw transdermal ethanol concentrations were calibrated to blood alcohol values using standardized ethanol solutions as a surrogate for blood alcohol concentration (BAC). KWJ has demonstrated a high degree of reproducibility in measurement sensitivity across several watch format devices.

3.2 Rationale and Purpose

In this proposed study, the objective is to further demonstrate the reliability of this printed electrochemical gas sensor in the form of a wearable device. This demonstration of reliability among human subjects is an essential part of product development. The monitor will be in a wristband or watch form, similar to a smartwatch. It will also have smartwatch features including measuring key physiological parameters (e.g., pulse) and eventually will have connectivity to apps on smartphones and other devices. The aim of the work is to provide a new, noninvasive transdermal alcohol monitor into the market. The transdermal alcohol monitoring market has few wearable products available and innovation has been lacking in this field. Developing a new wearable alcohol sensor could have many applications. For example, people interested in health and fitness who want to better track their alcohol intake. This may be particularly beneficial to

Calibration Study of a Wearable Noninvasive Blood Alcohol Monitor

Final V1.8 4.24.19

individuals who seek to reduce the risk of alcohol use by limiting peak BAL. This technology could be adapted for use in clinical trials where measurement of alcohol consumption is typically the primary outcome measure. Although the current “gold standard” for measuring alcohol use (the TLFB method) has acceptable reliability and validity, a wristwatch might offer advantages over the TLFB given the potential for precision of data that cannot be achieved with the estimation methods used with the TLFB. A wristwatch sensor may also offer an objective means of data collection that is less vulnerable to the risk of subject deception or intentional minimization. Additionally, there is a certain degree of subject reactivity to completing drinking assessments on a weekly basis that alters the course of drinking. If successful, this wristwatch may provide a means for assessing alcohol consumption without subjects reacting to the assessment methodology. This technology could also be adopted in many areas including clinical and medical treatment, employee wellness programs, alcohol, and as part of brief interventions that target at-risk drinkers.

4 Objectives

4.1 Study Objectives

The specific objective of this study is to determine whether the printed electrochemical gas sensor designed to measure BAL will be sensitive and reliable when compared to a standard measure of BAL taken by a breathalyzer (Intoximeter Alco-Sensor IV). If this sensor proves sensitive to changes in BAL and can reliably measure BAL relative to a “gold standard” method, there are significant opportunities to use this technology in consumer health applications and clinical research.

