4.2 Study Outcome Measures

4.2.1 Primary Outcome Measures

The primary outcome is the correlation in estimated BAL as measured by the breathalyzer and the wristwatch sensor during the second alcohol self-administration trial. BAL and wristwatch sensor data correlation will be analyzed by repeated measures correlation (rmcorr) analysis, as described in more detail in section 12.

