4.2.2 Secondary Outcome Measures

In addition to the determination of correlation between BAL and transdermal alcohol concentration (TAC) as measured by a reference breathalyzer and the developmental KWJ wrist device, respectively, we anticipate that Phase I of this study (the first alcohol self administration trial) will provide a means to determine the characteristic time lag between BAL and TAC [12] and furthermore allow development of a preliminary model for correcting TAC measurements for this lag.

5 Study Design

Calibration Study of a Wearable Noninvasive Blood Alcohol Monitor

Final V1.8 4.24.19

This is a device calibration study designed for healthy non-treatment-seeking drinkers. The drinking lab portion of this study is an adaptation of an established human laboratory self-administration procedures [13]. Subjects who consent to this study will complete two alcohol self-administration sessions, one in the Calibration phase (Phase I) of the study and one in the Validation phase (Phase II) of the study.

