12.1 Study Hypotheses and Planned Analyses

Calibration Phase I

The objective of the Phase 1 of this study is to use data obtained from subjects who have consumed alcohol in a controlled laboratory setting to develop a model of the relationship between BrAc and TAC measurements that will allow for the determination of estimated blood alcohol levels (BAL) from TAC data collected over extended periods of time.

The results of several studies support the expectation that for most subjects the time to reach peaked alcohol concentrations (Tmax) will be greater for TAC as compared BrAc values [20-21]. In contrast, maximal BrAc concentration (Cmax) values are expected to be smaller be for TAC values collected during test session as compared to those obtained for BrAC measurements. Nevertheless, if TAC values detected by the test device are directly related to blood alcohol levels there should be a strong correlation between the CMax for both TAC and BrAc measurements. Therefore, we hypothesize that for correlations between Cmax values for TAC and BrAc values should be have an r value of 0.8 or greater. A finding consistent with this hypothesis will provide evidence that the test alcohol monitor is able to detect TAC levels that are directly related to BAL.

Validation Phase

Validation Phase

TAC data collected during validation phase will be converted into predicted BAL values for individual subjects using the models developed in the Phase 1 of this investigation. Data obtained during the validation phase will be inspected to determine if there are differences in the sensitivity between the breathalyzer and the wristwatch sensor. Time concentration curves for BrAc and predicted BAL values will be produced for each subject. These curves will be examined to check whether there are any systematic differences between these two measures in the time needed to reach maximal concentration levels for each of the subjects (Tmax) and between the values obtained at the maximum concentration levels (Cmax).

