Given that BAL and BrAc are expected to be equivalent it is also hypothesized that there will be a strong correlation between Cmax and Tmax values. Pearson correlation coefficients for correlation analysis between both Cmax and Tmax determined from individual subjects' BrAc and BAL curves, therefore, are expected to be 0.8 or greater, with p values being less than 0.05.

Hypothesis	Planned Analyses
1. There will be a significant correlation between BrAc predicted BAL measures	Repeated measures correlation analysis of wristwatch TAC measurements and contemporaneous BAC measurements from breathalyzer.
2. There will be a significant correlation between Cmax and Tmax values obtained for paired BrAc and predicted BAL measurements.	Pearson correlation analysis for Tmax and Cmax values obtained for BrAc and predicted BAL data.

We expect that the results of this study will demonstrate the effectiveness of the developmental wristwatch transdermal alcohol sensor. Furthermore, these results and the developmental work to calibrate this wristwatch will contribute significant knowledge toward the understanding of reliable measurement of blood alcohol via transdermal routes.

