12.2 Sample Size Determination

Calibration Study of a Wearable Noninvasive Blood Alcohol Monitor

Final V1.8 4.24.19

Power analysis: Eight concurrent readings of breathe (BAL) and transdermal alcohol concentration (TAC) will be obtained from the wristwatch sensor and the breathalyzer starting 15 minutes after the start of subject alcohol consumption to the end of the 60 minute drinking session. An additional 20 concurrent readings will be collected during the 5 hour observation period in phase I, and an additional 12 concurrent readings in the 3-hour observation period in phase II. This means that a possible 28 (Phase I) or 20 (phase II) points may be available for this analysis if only pairs of data are used for which values for both devices exceed zero. However, the sensitivity of the wristwatch sensor in human subjects is currently unknown, and so fewer than 20 data points may be of use for our analysis.

Data will be analyzed using a repeated measures correlation (rcmm) procedure described by Bland and Altman [24] and Bakdash and Marisich [25]. For the wristwatch device to be considered to be useful the r value for the correction between BrAc and predicted BAL measures must exceed 0.9. Cohen [26] defines a large effect size as being $r=0.5$. Bakdash and Marish provide power curves for the rcmm procedure. These curves indicate that for a large effect size ($r=0.5$) that the power approach 99% when data from only 10 points are available for sample size of about 7. We anticipate a repeated measures correlation value of at least 0.8 and hope to observe a correlation of 0.9. Bakdash and Marisich [25] indicate the degrees of freedom for determining rcm values can be determined using the following equation:

$$Df = (\text{Number of subjects}-2) \times (\text{number of data points} - 1).$$

The degrees of freedom can be used to determine the corresponding sample size, with the degrees of freedom for standard tables of power analysis being equal to $N-2$ ($Df=N-2$). Using this relationship we use the Proc Power procedure for Pearson correlations in SAS to determine the power for 21 data points collected for 9 subjects and 10 datapoints for 5 subjects. In both of these analyses the calculated power value was > 0.995 for rcm of 0.8 or 0.9.

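### Sensitivity is part of the stated objective, but no outcome counts missed alcohol, and a watch blind below 0.02 g/dL can still exceed the r > 0.9 usefulness rule

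*Combined protocol and SAP*

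**What the plan says.** - **Objective (section 4.1).** The study is to determine whether the "gas sensor designed to measure BAL will be sensitive and reliable when compared to a standard measure of BAL". The next sentence speaks of responsiveness: "If this sensor proves sensitive to changes in BAL".
- **Outcomes (section 4.2).** "The primary outcome is the correlation in estimated BAL as measured by the breathalyzer and the wristwatch sensor" in the second session. The secondary outcome is to "determine the characteristic time lag between BAL and TAC" and to build a model that corrects for it.
- **Tests (section 12.1).** Repeated measures correlation, and "Pearson correlation analysis for Tmax and Cmax values obtained for BrAc and predicted BAL data". Section 12.2 adds AUC and Cmax correlations as a fallback if lag defeats the main analysis.
- **Sensitivity in the analysis plan (section 12.1, Validation Phase).** Data will be "inspected to determine if there are differences in the sensitivity between the breathalyzer and the wristwatch sensor". No statistic, denominator or criterion is given.
- **Usefulness rule (section 12.2).** r between breath alcohol and predicted BAL must exceed 0.9. Section 12.1 expects only more than 0.80; the stricter figure is used below.
- **Known uncertainty (section 12.2).** "the sensitivity of the wristwatch sensor in human subjects is currently unknown, and so fewer than 20 data points may be of use". The count of available points is described for the case in which "only pairs of data are used for which values for both devices exceed zero".
- **False positives (section 9, Zero BAL observation).** A one-hour zero-alcohol period checks that the watch does not read falsely high. There is no matching check for readings that are falsely zero.

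**The concern.** A correlation asks whether two series rise and fall together. It does not ask how often the watch shows nothing while the breathalyzer shows alcohol. The rise to about 0.05 g/dL and the fall from it dominate within-subject variation, so losing the low end of the curve may cost little in r. If pairs with a zero on either device were dropped, the missed readings would leave the analysis altogether.

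At stake is the claim the trial can make. The watch could be called useful, and the sensitivity part of the objective treated as met, with no summary of the levels at which it detects alcohol or of how often it fails to. Section 6.2 envisages using such a device to calculate the timing, frequency and quantity of drinking, which depends on detecting the start and the tail of an episode.

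**Working it through.** **1. The plan's own figures.** The plan gives no figure for detection. Its power figures reproduce.
- Pearson r = 0.8, n = 9, two-sided alpha 0.05 (sidedness assumed): simulation gives 0.820, against 0.82 stated.
- Repeated measures correlation, with the plan's Df = (subjects − 2) × (points − 1) and N = Df + 2: 9 subjects × 21 points gives Df = 7 × 20 = 140 and power of about 1.000. 5 × 10 gives Df = 3 × 9 = 27 and power 0.9999 at r = 0.8. Both exceed the stated 0.995.

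These are powers against zero correlation and say nothing about detection.

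**2. Inputs for the check.**
- From the documents: 9 completers; target peak 0.05 g/dL after one hour; three hours of Phase II observation; breath readings every 15 minutes, so 4 + 12 = 16 readings. Section 12.2 counts 8 + 12 = 20, and both counts were tried.
- Assumed: fall 0.015 g/dL per hour; blind zone below 0.02 g/dL; between-subject SDs; watch noise; no residual lag.

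**3. One noise-free subject.** Breath alcohol is 0.05t up to t = 1 hour, then 0.05 − 0.015(t − 1). The watch equals breath alcohol at 0.02 or above and is zero otherwise.
- Readings below 0.02: 0.0125 on the rise; 0.01625, 0.0125, 0.00875 and 0.005 on the fall. Missed: 5 of 16 = 31%.
- Sums: Σb = 0.4325, Σw = 0.3775, Σb² = 0.014578, Σw² = Σbw = 0.013900.
- Sbb = 0.014578 − 0.4325²/16 = 0.002887.
- Sww = 0.013900 − 0.3775²/16 = 0.004993.
- Sbw = 0.013900 − 0.4325 × 0.3775/16 = 0.003696.
- r = 0.003696 / √(0.002887 × 0.004993) = 0.973.

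On the 20-reading count, 7 of 20 (35%) are missed and r = 0.966. On both-above-zero pairs r = 1.000. Over peaks of 0.04 to 0.06 and falls of 0.010 to 0.020 g/dL per hour, noise-free r on all pairs stays between 0.936 and 0.985 for this simple cut-off.

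**4. Nine subjects with noise.** Peak SD is 0.0075 g/dL and fall SD 0.003 g/dL per hour; there are 16 readings and no lag. Ranges cover two forms of blind zone: a simple cut-off, and a response shifted and rescaled so that it starts from zero at the threshold.

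| Watch | Noise SD (g/dL) | r, all pairs | r, both above zero | Missed, breath > 0.005 |
|---|---|---|---|---|
| No blind zone | 0.003 | about 0.98 | about 0.975 | almost none |
| Blind below 0.02 | 0.003 | 0.93–0.95 | 0.96–0.98 | 28–29% |
| Blind below 0.025 | 0.003 | 0.88–0.92 | 0.95–0.985 | about 40% |

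At SD 0.003 the watch blind below 0.02 exceeds 0.9 in about 94% or more of simulated studies. After the both-above-zero filter its r can equal or slightly exceed that of the watch with no blind zone.

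**5. Where the pass fails.**
- Noise SD 0.005, blind below 0.02: r > 0.9 in 83 to 100% of studies on all pairs (repeat simulations put the lower end at 78 to 83%) and in 33 to 100% after the filter, depending on the form of the blind zone.
- A 15-minute uncorrected lag at SD 0.003: r is 0.82 to 0.84 on all pairs and about 0.75 filtered, so no study passes. The same lag also fails a watch with no blind zone (r about 0.84 to 0.86).

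**The case against.** Four points on the other side have weight.

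- **The pass depends on assumptions.** A reader might infer that a watch blind below 0.02 g/dL always passes. The documents do not support that. The blind zone, noise and fall rate are not in them, and the pass needs low noise and a good lag correction. Lag is the problem the plan most expects. This stands, and limits the claim to saying that such a watch can pass. The lag result does not rescue r as a measure of sensitivity, because lag fails sighted and blind watches alike.
- **The filter is not a rule.** A reader might infer that the plan requires both devices to exceed zero. Section 12.2 says so only conditionally, when counting possible data points. Section 12.1 describes the analysis data as covering every time-point with a breath measurement. This stands. The result on all pairs does not need the filter.
- **Correlation does register blindness to some degree.** Section 4.1 also glosses sensitivity as response to changes in BAL, which a within-subject correlation partly measures. With blindness below 0.025 g/dL, r on all pairs falls to 0.88 to 0.92. It would be too strong to say that r ignores missed alcohol. Even so, a watch fixed at zero up to 0.02 g/dL does not respond to change over 40% of the target range (0.02/0.05) and can still pass.
- **Some information on timing will exist.** A reader might infer that the trial could not learn how late the watch responds. Lag is a secondary outcome, Tmax is compared, and each subject's time curves will be examined, so a flat start or tail would be visible. What is missing is a prespecified summary, not the raw information.

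**Conclusion.** The point holds in a conditional form. Section 4.1 makes sensitivity part of the specific objective, yet nothing in sections 4.2 or 12 quantifies missed alcohol, and the informal inspection in section 12.1 has no statistic. That gap is plain from the text and needs no simulation.

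The simulation shows that the r > 0.9 rule does not fill the gap. With noise SD 0.003 g/dL and no residual lag, a watch that misses over a quarter of readings above 0.005 g/dL scores 0.93 to 0.98, against about 0.975 to 0.98 for one that misses almost none. Under higher noise or residual lag the blind watch may fail, but mainly because r then reflects noise and lag. In neither case does r answer the sensitivity question. The sizes rest on the assumed blind zone, fall rate, spread and noise; they illustrate what can happen and do not predict how this device will behave.

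**What to change.** Replace the unspecified inspection in section 12.1 with a prespecified Phase II secondary outcome, listed also in section 4.2.2:

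- Use all readings with breath alcohol above zero, with no both-above-zero filter.
- Report the proportion at which the watch exceeds an upper limit taken from its own zero-BAL hour, for example mean + 3 SD. State whether raw TAC or predicted BAL is used.
- Report it overall and by a few breath-alcohol bands, for example up to 0.010, 0.011–0.020, 0.021–0.030 and above 0.030 g/dL, with a 95% confidence interval from resampling subjects.
- Report the time from first positive breath reading to first watch detection.
- State that r > 0.9 alone does not answer the sensitivity part of the objective.

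The cost is a few lines of text and one table from data already planned; no procedure is added. The downside is imprecision. On the step 3 curve, 9 subjects × 16 readings = 144 readings would split into 18, 36, 27 and 63 across the four bands, clustered in nine people, so intervals will be wide. The result may also look less favourable than r.
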